16.1.6.1. Hematology

Blood will be analyzed for the following hematology parameters: platelet, RBC, and WBC counts; automated differential (neutrophils, lymphocytes, monocytes, eosinophils, basophils); hemoglobin; hematocrit; and RBC indices (mean corpuscular volume, mean corpuscular hemoglobin, and mean corpuscular hemoglobin concentration).

The timing of hematology assessments is described in the Schedules of Assessments (Section 9).

16.1.6.2. Blood Chemistry

Blood samples will be analyzed for the following clinical chemistry parameters: blood urea nitrogen; creatinine; glucose; sodium; phosphorus; potassium; chloride; total carbon dioxide; total calcium; magnesium; AST; ALT; gamma-glutamyltransferase; alkaline phosphatase; lactate dehydrogenase; total, direct, and indirect bilirubin; uric acid; albumin; and total protein. Considering that indirect bilirubin is calculated from total and direct bilirubin values, indirect bilirubin results will not be available if direct bilirubin is below the limit of quantification.

Serum follicle-stimulating hormone level and estradiol concentrations will be measured at screening for postmenopausal female subjects to confirm their postmenopausal status.

The timing of chemistry assessments is described in the Schedules of Assessments (Section 9).

16.1.6.3. Coagulation

Blood samples will be analyzed for prothrombin time, international normalized ratio, and partial thromboplastin time.

The timing of coagulation assessments is described in the Schedules of Assessments (Section 9).

16.1.6.4. Urinalysis and Urine Chemistry

Urinalysis will include specific gravity, pH, glucose, protein, blood, and ketones. A microscopic examination of urine samples will be performed only on abnormal findings.

Urine samples will also be sent to the pathology laboratory to measure protein and creatinine in order to calculate the urine protein:creatinine ratio.

The timing of urinalysis and urine chemistry assessments is described in the Schedules of Assessments (Section 9).

16.1.6.5. Virus Serology

Blood samples collected at screening will be analyzed for HIV-1, HIV-2, HBsAg, and HCV antibody titers.

Hepatitis B surface antigen testing is required for all subjects prior to enrollment. Subjects with positive HBsAg will not be enrolled.

For subjects with negative HBsAg, the following testing algorithm will be required:

- 1. If hepatitis B core antibody (HBcAb) is negative, the subject is eligible to enroll.
- 2. If HBcAb is positive, the hepatitis B surface antibody (HBsAb) will be tested.
 - a. If both HBcAb and HBsAb are positive, the subject is eligible to enroll.
 - b. If HBcAb is positive and HBsAb is negative, the subject will not be enrolled.

16.1.6.6. Drug and Alcohol Screen

A urine sample for drug screen will be analyzed for the following compounds: amphetamines; barbiturates; benzodiazepines; cocaine; methadone; opiates; phencyclidine; methamphetamine; 3,4-methylenedioxy-methamphetamine and tetrahydrocannabinol (cannabinoids). Alcohol breath tests will be performed. If positive prior to dosing, dosing will not proceed.

Timing of urine drug and alcohol breath tests are described in the Schedules of Assessments (Section 9).

16.1.6.7. Pregnancy Testing

Pregnancy testing (beta human chorionic gonadotrophin) will be performed in all female subjects (Section 17.8). The timing of pregnancy testing is described in Schedules of Assessments (Section 9).

16.1.6.8. Tuberculosis

Blood samples for a QuantiFERON®-TB test will be collected as described in the Schedules of Assessments (Section 9).

16.1.6.9. Complement Activity

A suitable assay for determining complement activity, such as CAP ELISA/C5 (hemolysis) inhibition, will be performed at screening to confirm subjects do not have a complement deficiency. Subjects found to be complement deficient will be excluded from participating in the study.

Blood samples will be collected at baseline and during follow-up for measurement of CH50 activity using an in vitro liposome immunoassay to confirm normalization of complement activity. If a normal CH50 result is obtained from a subject's CH50 sample collected during

follow-up, antibiotic prophylaxis can be stopped and the additional scheduled CH50 samples are not required. If the last CH50 sample is not normal, the baseline sample may be analyzed (see Schedules of Assessments in Section 9) and the investigator will contact the subject regarding whether antibiotic prophylaxis must be further extended.

16.1.6.10. Serum Bactericidal Antibody

An SBA titer against meningococcus Group A, C, W135, and Y will be performed at screening. Titer measurements will be used to exclude subjects without an immune response from being dosed.

17. ADVERSE EVENT MANAGEMENT

The investigator is responsible for detecting, assessing, documenting and reporting all AEs. All AEs will be recorded from the signing of informed consent until study completion. There is no time limit for SAEs that are considered causally related.

All observed or volunteered AEs, regardless of causal relationship, must be reported and recorded in the data capture system. Adverse events reported by the subject and/or parent or legal guardian, and/or identified in response to an open-ended question from study personnel, or revealed by observation, physical examination, or other study procedures must be collected and recorded.

17.1. Definition of an Adverse Event

An AE is defined as any unfavorable and unintended sign (eg, including an abnormal laboratory finding), symptom, or disease temporally associated with the use of a medicinal product or procedure, whether or not considered related to the medicinal product or procedure, which occurs during the course of the clinical study.

Exacerbations of a chronic or intermittent pre-existing condition, including either an increase in frequency and/or intensity of the condition, are all to be considered AEs.

Abnormal test findings may be considered AEs. If an abnormal laboratory value is identified, investigators are strongly encouraged to report a diagnosis, or a sign or symptom, rather than an isolated abnormal test value. An abnormal test finding should be documented as an AE if **any of the following** conditions are met:

- Is associated with a sign or symptom
- Requires additional diagnostic testing (repeat tests are not considered additional testing)
- Requires a medical or surgical intervention
- Leads to a change in study dosing outside of the protocol-defined dosing or leads to discontinuation from the study
- Requires significant additional treatment
- Does not meet any of the conditions above; however, the investigator or sponsor considers the result clinically significant or meeting the definition of an AE.

This definition also includes the signs or symptoms resulting from:

- Drug overdose
- Drug withdrawal
- Drug misuse
- Drug interactions
- Extravasation

- Exposure during pregnancy
- Exposure via breastfeeding
- Medication error
- Occupational exposure

An AE does not necessarily include the following:

- Medical or surgical procedures (eg, surgery, endoscopies, tooth extraction, transfusion); the condition that leads to the procedure is the AE (eg, laparoscopic cholecystectomy is the procedure or treatment for an SAE of necrotic gall bladder)
- Pre-existing diseases or conditions present or detected prior to the screening evaluation that do not worsen
- Situations where an untoward medical occurrence has not occurred (eg, hospitalization for elective surgery if planned prior to the start of the study, social and/or convenience admissions)

17.2. Definition of a Serious Adverse Event

Any AE that fulfills any 1 of the criteria listed below must be recorded as an SAE.

An SAE is described as any untoward medical occurrence that, at any dose:

- 1. Results in death
- 2. Is life threatening^a
- 3. Requires hospitalization or prolongation of hospitalization^b. Hospitalization does not necessarily include the following:
 - Rehabilitation/hospice/nursing facility
 - Emergency Room visit less than 24 hours
 - Elective or preplanned admission/surgery/day surgery
 - Protocol-specified admission
 - Admission for a pre-existing condition not associated with either a new AE or with worsening of a pre-existing AE
- 4. Results in persistent or significant disability/incapacity
- 5. Is a congenital anomaly/birth defect
- 6. Is an important medical event^c

^a The term "life threatening" in the definition of "serious" refers to an event in which the subject was at risk of death at the time of the event; it does not refer to an event which hypothetically might have caused death if it were more severe.

^b Hospitalization requires inpatient admission or prolongation of an existing hospitalization. The AEs that are associated with hospitalization or prolongation of hospitalization are considered SAEs.

^c Important medical event: Medical and scientific judgment should be exercised in deciding whether expedited reporting is appropriate in other situations, such as important medical events that may not be immediately life threatening, or result in death or hospitalization, but may jeopardize the subject or may require intervention to

prevent 1 of the other outcomes listed in the definition above. These should also usually be considered serious. Examples of such events are intensive treatment in an emergency room or at home for allergic bronchospasm; blood dyscrasias or convulsions that do not result in hospitalization; or development of drug dependency or drug abuse.

Severity and seriousness must be differentiated. Severity describes the intensity of an AE, while the term seriousness refers to an AE that has met the criteria for an SAE, as described above.

17.3. Severity Assessment

All AEs will be graded according to criteria from CTCAE v4.03, published June 14, 2010.

- Grade 1: Mild (awareness of sign or symptom, but easily tolerated)
- Grade 2: Moderate (discomfort sufficient to cause interference with normal activities)
- Grade 3: Severe (incapacitating, with inability to perform normal activities)
- Grade 4: Life threatening
- Grade 5: Fatal

Changes in the severity of an AE should be documented to allow an assessment of the AE duration at each level of intensity to be evaluated. Adverse events characterized as intermittent require documentation of onset and duration of each episode, if the severity of the intermittent event changes.

17.4. Causality Assessment

An investigator causality assessment must be provided for all AEs (both nonserious and serious). This assessment must be recorded in the data capture system and on any additional forms, as appropriate. The definitions for the causality assessments are as follows:

- Not related (unrelated): This relationship suggests that there is no association between the investigational product and the reported event.
- Unlikely related: This relationship suggests that the clinical picture is highly consistent with a cause other than the investigational product, but attribution cannot be made with absolute certainty, and a relationship between the Investigational Product and AE cannot be excluded with complete confidence.
- Possibly related: This relationship suggests that treatment with the investigational
 product may have caused or contributed to the AE, ie, the event follows a reasonable
 temporal sequence from the time of drug administration, and/or follows a known
 response pattern to the investigational product, but could also have been produced by
 other factors.
- Probably related: This relationship suggests that a reasonable temporal sequence of the event with the investigational product administration exists, as well as the likely association of the event with the investigational product. This will be based upon the known pharmacological action of the investigational product, known or previously reported adverse reactions to the investigational product or class of drugs, or judgment based on the investigator's clinical experience.

Definitely related: Temporal relationship to the investigational product. Other
conditions (concurrent illness, concurrent medication reaction, or
progression/expression of disease state) do not appear to explain event, corresponds
with the known pharmaceutical profile, improvement on discontinuation,
reappearance on rechallenge.

17.5. Outcome

For all AEs, regardless of causal relationships, the investigator must follow up regarding the outcome of the event until the event or sequelae either resolve or stabilize. Adverse event outcomes must be recorded in the data capture system and on any additional forms, as appropriate.

If a subject experiences an SAE with an outcome of death, the following procedures are to be performed:

- The SAE resulting in death should have an outcome documented as death/fatal, with an end date being the date of death.
- If the subject had additional AE/SAEs that were ongoing at the time of death, these events would be documented as ongoing with no end date.
- Only 1 event should have an outcome of death/fatal, unless an autopsy report or investigator states otherwise.

17.6. Recording Adverse Events

All observed or volunteered AEs, regardless of dose cohort or causal relationship, must be reported as described in Section 17.4 (Causality Assessment).

For all AEs, the investigator must do the following:

- 1. Determine the AE outcome
- 2. Determine if the event meets criteria for an SAE
- 3. Assess AE severity
- 4. Determine AE causality

Adverse events must be documented in clear, unambiguous medical terms. Study personnel are advised not to use abbreviations or acronyms.

For each AE, record on the data capture system only the diagnosis; do not report the characteristic signs and symptoms of the diagnosis as additional AEs.

If a diagnosis is not available, record each sign and symptom as an AE; when a diagnosis becomes available, study personnel are to update the source document and the data capture system with the relevant diagnosis only.

For medical or surgical procedures (eg, surgery, endoscopies, tooth extraction, transfusion), the condition/diagnosis that leads to the procedure should be recorded as the AE (eg, laparoscopic cholecystectomy is the procedure or treatment for an SAE of necrotic gall bladder).

All AEs that later increase in frequency and or severity (medical and scientific judgment should be exercised by the investigator) will be considered new AEs, and will be recorded on a new line in the data capture system.

Withdrawal due to an AE or SAE must be clearly differentiated from withdrawal due to other reasons.

17.7. Reporting of Serious Adverse Event(s) to the Sponsor

All AEs must be assessed by the investigator to determine if they meet criteria for an SAE. All SAEs must be reported to Alexion or designee immediately, or within 24 hours of the investigator and/or study site staff becoming aware of the event, regardless of the presumed relationship to the study drug.

The investigator must complete, sign, and date the SAE pages, verify the accuracy of the information recorded on the SAE pages with the corresponding source documents, and send a copy via E-mail or fax to the contact information provided below:

E-mail: PPD
Fax: PPD

When further information becomes available, the SAE should be updated with the new information and reported immediately via the same contact information.

Additional follow-up information, if required or available, should be entered into the case report form and sent to sponsor within 24 hours of the investigator or study site staff becoming aware of this additional information via the reporting process outlined above. These reporting timelines need to be followed for all initial SAE cases and follow-up versions of the initial cases.

For all SAEs, the investigator must provide the following:

- Appropriate and requested follow-up information in the time frame detailed above
- Causality of the serious event(s)
- Outcome of the serious event(s)
- Medical records and laboratory/diagnostic information

17.8. Exposure During Pregnancy and Lactation

Pregnancy data will be collected during this study for all subjects.

For all Alexion products, both in development or postapproval, exposure during pregnancy must be recorded and followed. Exposure during pregnancy, also called exposure in utero, can be the result of either maternal exposure or transmission of drug product via semen following paternal exposure.

If a female subject participating in this study or a male subject's female partner becomes or is found to be pregnant while being treated or exposed to study drug, the investigator must submit the "Pregnancy Reporting and Outcome/Breast Feeding Form" to Alexion or designee via the same method as SAE reporting. Female subjects who become pregnant will be discontinued from dosing, but will continue to be followed for safety where feasible. Male subjects may continue in

the study if an accidental pregnancy of their female partner occurs despite adequate contraception.

The female subject should be followed until the outcome of the pregnancy is known (spontaneous miscarriage, elective termination, normal birth or congenital abnormality), even if the subject discontinues study drug or discontinues from the study. When the outcome of the pregnancy becomes known, the form should be updated and returned to Alexion or designee. If additional follow-up is required, the investigator will be requested to provide the information.

Pregnancy in itself is not regarded as an AE, unless there is a suspicion that investigational product may have interfered with the effectiveness of a contraceptive medication. However, complications of pregnancy and abnormal outcomes of pregnancy are AEs, and many may meet criteria for an SAE. Complications of pregnancy and abnormal outcomes of pregnancy, such as ectopic pregnancy, spontaneous abortion, intrauterine fetal demise, neonatal death, or congenital anomaly, would meet the criteria of an SAE and therefore should be reported as an SAE. Elective abortions without complications should not be handled as an AE.

Exposure of an infant to an Alexion product during breastfeeding should also be reported on the "Pregnancy Reporting and Outcome/Breast Feeding Form." Any AEs an infant experiences following breastfeeding are to be reported to Alexion or designee.

17.9. Reporting Requirements

This protocol will use the current Investigator's Brochure as the Reference Safety Document. The expectedness and reporting criteria of an SAE will be determined by Alexion, based on the Reference Safety Document.

17.9.1. **Sponsor**

The sponsor or legal representative is responsible for notifying the relevant regulatory authorities of SAEs meeting the reporting criteria. The sponsor will inform the investigator of any safety issues that may arise during the course of the study. Any safety issue which may alter the current benefit-risk assessment of the study drug will be reported by the sponsor (or delegate) on an expedited basis to Health Authorities, Ethics Committees, and the investigator.

17.9.2. Investigator

The investigator must fulfill all local regulatory requirements for investigators conducting clinical studies. It is the investigator's responsibility to notify the IRB or IEC of all reportable SAEs that occur. Alexion will notify investigators of all unexpected, serious, drug-related events (7/15 Day Safety Reports) that occur during the clinical study. The investigator is responsible for notifying the IRB or IEC of these additional SAEs.

Adverse events are recorded in the case report form, and are retrieved by or submitted to the sponsor at regular monthly intervals, or more frequently during the course of the investigation.

18. DATA COLLECTION

All clinical raw data will be recorded promptly, accurately, and legibly, either electronically or on paper. A detailed list of the type (electronic or paper) and location for all source data will be included in the Trial Master File. All raw data will be preserved in order to maintain data integrity. The investigator or designee will assume the responsibility of ensuring the completeness, accuracy, and timeliness of the clinical data.

At each scheduled monitoring visit, the investigator or designee will cooperate with the sponsor's representative(s) for the periodic review of study documents to ensure the accuracy and completeness of the data.

Electronic consistency checks and manual review will be used to identify any errors or inconsistencies in the case report form. This information will be provided to the respective study sites by means of electronic or manual queries.

The investigator or designee will prepare and maintain adequate and accurate source documents (medical records, ECGs, AE and concomitant medication reporting, raw data collection forms) designed to record all observations and other pertinent data for each subject receiving study drug.

The investigator will allow sponsor representatives, contract designees, authorized regulatory authority inspectors, and the IRB/IEC to have direct access to all documents pertaining to the study.

19. STATISTICS

19.1. Statistical Analysis Plan Summary

A formal statistical analysis plan will be developed and finalized before database lock.

Statistical analyses will be performed by Richmond Pharmacology Ltd. Pharmacokinetic parameters will be calculated by Nuventra Pharma Sciences using Phoenix[®] WinNonlin[®] 6.3 or higher (Certara, Inc, Princeton, NJ). Tables, figures, and listings will be produced using an automated system (Certara L.P.).

Any deviations from the planned analyses will be described in the final integrated clinical study report.

19.2. Analysis Populations

The safety population will consist of all subjects who receive at least 1 dose of study drug. Subjects in this population will be used for the safety analysis.

The PK population will consist of all subjects who have sufficient serum concentration data to enable the calculation of PK parameters. The PK population will be used for PK summaries.

The PD population will consist of all subjects who have sufficient total and free C5 concentration data, cRBC hemolysis data, or other data measuring C5 activation to enable the evaluation of the PD effects. The PD population will be used for PD summaries.

The immunogenicity analysis population will consist of all subjects who have a predose and postdose ADA sample collected.

19.3. Sample Size and Power

The sample size of 4 subjects in each of the single-dose cohorts (Cohorts 1 and 2) and 6 to 8 subjects in the 800 mg multiple-dose cohort will allow for the characterization of the central tendency of PK parameters as they relate to ALXN1210 and to gain initial knowledge of PK/PD relationships in Japanese subjects. To ensure future modeling and simulations are accurate, it is preferred to estimate the PK parameters with a maximum imprecision of < 25% following the IV administration of ALXN1210. Six subjects in Cohort 3 will provide 23.3% maximum imprecision (Table 17) for the estimation of area under the serum concentration versus time curve from time 0 extrapolated to infinity (AUC $_{\infty}$), in terms of the relative distance of the lower 90% confidence limit from the observed PK parameter that will be obtained with 80% assurance and assuming the within-subject SD of the log-transformed AUC $_{\infty}$ is as much as 0.19.

Table 17: Estimation of the Maximum Imprecision in the Estimate of PK Parameters for Selected Sample Sizes

Number of Subjects on Active	Maximum Imprecision (%)
4	33.6
6	23.3
8	18.9

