Follow-up	the following time points: Day 113 (4 hr and 8 hr), Day 114 (24 hr), Day 115 (48 hr), Day 117 (96
(Days 113-298)	hr), Day 120 (168 hr), Day 127 (336 hr), Day 134 (504 hr), Day 141 (672 hr), Day 148, Day 155,
	Day 162, Day 169, Day 183, Day 197, Day 225, Day 253, and Day 298

Immunogenicity:

Table 3s: Collection Time Points for Serum Samples for Analyses of Antidrug Antibodies to ALXN1210

Collection Time Points for Cohort 1		
(Days 1-120)	Pre-dose on Day 1, and on Day 15, Day 29, Day 57, Day 90, and Day 120	
Collection Time Po	oints for Cohort 2	
(Days -1-140)	Pre-dose on Day 1, and on Day 15, Day 29, Day 57, Day 90, Day 120, and Day 140	
Collection Time Points for Cohort 3		
Periods 1 to 5	Pre-dose on Day 1; on Day 8, Day 15, and Day 22 after Dose 1; on Day 29 prior to Dose 2 and on Day	
(Days 1-298)	43 after Dose 2; on Day 57 prior to Dose 3 and on Day 71 after Dose 3; on Day 85 prior to Dose 4 and	
	on Day 99 after Dose 4; on Day 113 prior to Dose 5 and on Day 120, Day 141, Day 169, Day 197,	
	Day 225, Day 253, and Day 298 following Dose 5	

Please refer to the Study Operation Manual (SOM) for time windows for collection, and to the laboratory manual for details on sample collection including blood volume requirements.

No more than 470 mL of blood will be taken within each 16-week period in accordance with the guidance of NHS Blood and Transplant (http://www.blood.co.uk/about-blood/how-the-body-replaces-blood/).

Statistical methods:

The sample size of 4 subjects in each of the single-dose cohorts (Cohorts 1 and 2) and 6 to 8 subjects in the 800 mg multiple-dose cohort will allow for the characterization of the central tendency of PK parameters as they relate to ALXN1210 and to gain initial knowledge of PK/PD relationships in Japanese subjects. To ensure future modeling and simulations are accurate, it is preferred to estimate the PK parameters with a maximum imprecision of < 25% following the IV administration of ALXN1210. Six subjects in Cohort 3 will provide 23.3% maximum imprecision for the estimation of area under the serum concentration versus time curve from time 0 extrapolated to infinity (AUC $_{\infty}$), in terms of the relative distance of the lower 90% confidence limit from the observed PK parameter that will be obtained with 80% assurance and assuming the within-subject SD of the log-transformed AUC $_{\infty}$ is as much as 0.19.

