8.3. Dose Rationale

The geometric mean (CV%) ALXN1210 half-life in Study ALXN1210-HV-101 ranged from 30.8 (10.2%) to 32.4 (16.2%) days over the studied doses. Following single IV infusion (200-and 400-mg) dose administrations of ALXN1210 to healthy volunteers, all studied PD variables showed dose-dependent changes from baseline that recovered back to baseline. The effect of ALXN1210 on these PD variables was immediately evident after EOI. At the EOI, the mean free C5 serum concentrations and cRBC hemolysis activity were inhibited by > 99% and > 97%, respectively. In ongoing Study ALXN1210-HV-102, ALXN1210 IV doses of 400 every 4 weeks and 800 mg every 4 weeks are being studied to assess PK, PD, and tolerability in healthy volunteers. The PK, PD, and tolerability data from the non-Japanese studies (Study ALXN1210-HV-101 and Study ALXN1210-HV-102) will be compared with the data from the current study to assess PK, PD, and tolerability bridging between Japanese and non-Japanese healthy volunteers. In the current study, dose escalation (400 mg to 800 mg single dose) and dose progression (800 mg single dose to 800 mg multiple dose) will be decided upon SRC review of the safety and tolerability data from the preceding cohort.

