#### 4.2. Sample Size and Power

The sample size of 4 subjects in each of the single-dose cohorts (Cohorts 1 and 2) and 6 to 8 subjects in the 800 mg multiple-dose cohort will allow for the characterization of the central tendency of PK parameters as they relate to ALXN1210 and to gain initial knowledge of PK/PD relationships in Japanese subjects. To ensure future modeling and simulations are accurate, it is preferred to estimate the PK parameters with a maximum imprecision of < 25% following the IV administration of ALXN1210. Six subjects in Cohort 3 will provide 23.3%

maximum imprecision (Table 1) for the estimation of area under the serum concentration versus time curve from time 0 extrapolated to infinity (AUC $\infty$ ), in terms of the relative distance of the lower 90% confidence limit from the observed PK parameter that will be obtained with 80% assurance and assuming the within-subject SD of the log-transformed AUC $\infty$  is as much as 0.19.

Table 1:	Estimation of the Maximum Imprecision in the Estimate of PK	
	Parameters for Selected Sample Sizes	

Number of Subjects on Active	Maximum Imprecision (%)
4	33.6
6	23.3
8	18.9

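### The printed maximum imprecision (33.6%, 23.3%, 18.9% for n = 4, 6, 8) does not follow from its stated definition and SD, which give 24.3%, 17.2%, 14.0%

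*Protocol*

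**What the plan says.** Protocol 19.3 sets the aim: "it is preferred to estimate the PK parameters with a maximum imprecision of < 25% following the IV administration of ALXN1210". The measure is the "relative distance of the lower 90% confidence limit from the observed PK parameter that will be obtained with 80% assurance", and the calculation proceeds by "assuming the within-subject SD of the log-transformed AUC" (to infinity) "is as much as 0.19". Protocol Table 17 then lists 33.6%, 23.3% and 18.9% for 4, 6 and 8 subjects. SAP 4.2 repeats the definition and SD, and its Table 1 has the same three figures: "Six subjects in Cohort 3 will provide 23.3" per cent. The synopsis gives the six-subject result: "Six subjects in Cohort 3 will provide 23.3% maximum imprecision for the estimation of area under the serum concentration".

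No formula, software or source for 0.19 is given. The documents contain no between-subject SD for AUC. Protocol 8.3 does give variability from the earlier single-dose study, but for half-life: it "ranged from 30.8 (10.2%) to 32.4 (16.2%) days over the studied doses", with the CVs in brackets.

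**The concern.** The text supplies everything needed to calculate the imprecision: a confidence level, an assurance, an SD on the log scale and the sample sizes. The result should therefore be reproducible, and it is not. The printed figures are roughly 1.35 to 1.4 times the recomputed ones (33.6/24.3 = 1.38, 23.3/17.2 = 1.35, 18.9/14.0 = 1.35).

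The SD label is a second problem. Cohort 1 and 2 subjects receive one dose, and all Cohort 3 subjects receive the same regimen. Each subject contributes one AUC to a cohort mean, and the spread that drives the precision of that mean is between subjects. A within-subject SD is the wrong component and would normally be the smaller one.

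The 23.3% is the only numerical support for the Cohort 3 size, and it appears in three places. Protocol 19.3 ties the target to later modelling and simulation, and protocol 8.3 plans a comparison with non-Japanese data, so readers may rely on the precision statement.

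**Working it through.** **Inputs** (protocol 19.3, repeated in SAP 4.2): lower 90% confidence limit, read as the lower end of a two-sided 90% interval (5% per tail); assurance 80%; log-scale SD 0.19; n = 4, 6, 8.

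**Formula.** For a t interval on the log scale, the distance from estimate to lower limit that will not be exceeded with 80% probability is

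h = t(0.95, n−1) × SD × √[χ²(0.80, n−1)/(n−1)] / √n, and imprecision = 1 − exp(−h).

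**Stated definition at SD 0.19**

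| n | t(0.95, n−1) | √[χ²(0.80)/(n−1)] | h | Recomputed | Printed |
|---|---|---|---|---|---|
| 4 | 2.353 | 1.244 | 0.2781 | 24.3% | 33.6% |
| 6 | 2.015 | 1.207 | 0.1887 | 17.2% | 23.3% |
| 8 | 1.895 | 1.183 | 0.1506 | 14.0% | 18.9% |

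For n = 6: 2.015 × 0.19 × 1.207/√6 = 0.1887, and 1 − exp(−0.1887) = 17.2%. A simulation of 1,000,000 samples per row gives the same 80th percentiles. At SD 0.19 the chance of an imprecision at or below the printed value is 98% to 99%, not 80%.

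**Could 0.19 be rounded?** SDs of 0.185 to 0.195 give 23.7–24.8%, 16.8–17.6% and 13.6–14.3%. No.

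**Could only the SD be mistyped?** Solving for the SD that yields each printed value ± 0.05 points gives 0.2792–0.2803 (n = 4), 0.2664–0.2677 (n = 6) and 0.2635–0.2651 (n = 8). The ranges do not overlap, so no single SD works under the stated definition.

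**Other readings at SD 0.19, 80% assurance** (n = 4 / 6 / 8):
- one-sided 90% lower limit: 17.6 / 12.9 / 10.6%
- lower end of a two-sided 95% interval: 31.3 / 21.4 / 17.1%
- distance to the upper limit: 32.1 / 20.8 / 16.3%
- SD multiplied by √2: 32.5 / 23.4 / 19.2%

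None matches all three rows.

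**Formulas that do fit, neither of them stated.** The half-width of the two-sided 90% interval relative to the geometric mean, without assurance, is sinh[t(0.95, n−1) × SD/√n]. It gives 33.6 / 23.3 / 18.9% for any SD from 0.2801 to 0.2808, but 22.5 / 15.7 / 12.8% at 0.19. The upper-limit distance with a √2 factor and the expected sample SD in place of 80% assurance also gives 33.6 / 23.3 / 18.9%, at SD 0.189; at 0.190 it gives 33.8 / 23.4 / 19.0%. Since two different departures from the text both fit, the origin of the table cannot be settled from the documents.

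**Sensitivity to the SD, stated definition** (between-subject SD of log AUC is an assumption):

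| SD | n = 6 | n = 8 |
|---|---|---|
| 0.15 | 13.8% | 11.2% |
| 0.20 | 18.0% | 14.7% |
| 0.25 | 22.0% | 18.0% |
| 0.30 | 25.8% | 21.2% |

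The 25% limit is reached at SD 0.197 (n = 4), 0.290 (n = 6) and 0.363 (n = 8). The half-life CVs in protocol 8.3 convert by √ln(1+CV²) to log-SDs of 0.102 and 0.161. They lie below these limits but do not measure AUC variability.

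**The case against.** The strongest reply is that nothing depends on this. The target is only a preference, the primary objective is safety, and PK is summarised descriptively. AUC to infinity is not among the listed PK endpoints in protocol 7.2 or SAP 2.2, and the only planned 90% interval is for optional dose proportionality on other parameters. At SD 0.19 the printed figures are pessimistic, so the error does not flatter the design. All of this stands and limits the weight of the point.

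A second reply is that the definition is not fully determined, because a lower 90% limit can also be read as one-sided. That is fair, and it means 24.3 / 17.2 / 14.0% should not be printed before sidedness is confirmed. It does not rescue the table: the one-sided reading moves further from it.

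Third, the plan makes its precision claim only for six subjects in Cohort 3 and never says that four meet the target. This is also correct. The four-subject contrast shows that text and table can lead to opposite readings, but no decision in the plan turns on it.

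Finally, within-subject may be a slip of wording for a between-subject SD. That cannot be excluded, which is why the source is needed.

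**Conclusion.** The concern holds. As written, the table and its description cannot both be right: the stated definition at 0.19 gives 24.3%, 17.2% and 14.0% against the printed 33.6%, 23.3% and 18.9%, and changing the SD alone does not reconcile them. The replacement values assume a two-sided 90% interval, one log AUC per subject, approximate normality on the log scale, and 0.19 as the between-subject SD.

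The Cohort 3 size is not undermined. Six subjects meet the preferred limit as printed (23.3%) and under the stated definition at 0.19 (17.2%). Even at the larger SD of 0.2805 they meet it under the stated definition (24.3%). They would miss it under that definition only if the between-subject SD reached about 0.29. At n = 4 the printed 33.6% misses the limit, while the stated definition just meets it, and only up to an SD of 0.197. Safety analysis and enrolment are unaffected. This should be corrected because a stated design figure cannot be reproduced and the remedy is cheap.

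**What to change.** Confirm four things with whoever produced the table: the formula (including one- or two-sided limit and whether assurance was applied), the SD value, whether it is within- or between-subject, and its source. Then amend the synopsis, protocol 19.3 and SAP 4.2 together:

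1. If the stated definition with a two-sided interval is confirmed, and 0.19 is a between-subject SD, print 24.3%, 17.2% and 14.0% (17.2% in the synopsis) and correct the SD label. If the limit was meant as one-sided, the corresponding values are 17.6%, 12.9% and 10.6%.
2. If another formula or SD produced the table, keep the table and restate the definition, assurance and SD to match it.
3. If 0.19 is truly within-subject, recompute with a between-subject SD of log AUC and cite its source.

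The cost is one sentence and, if needed, one three-row table in each document, plus one sentence in the synopsis. No change to sample size or enrolment is needed.
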